## 7.3 Covariates and Subgroups

Since the purpose of the study is to identify patient subgroups that differentially respond to the four treatments, our analysis will explore many treatment-covariate interactions. Table 2 and 3 list the expected treatment modifiers, which are the primary covariates of interest, for the light and deep phenotype measures, respectively. The light phenotype table also describes each variable's expected mechanistic role (treatment modifier versus treatment mediator). For additional details, please see Section 18.1 of the UM BACPAC clinical trial protocol.

Table 2 Hypothesized light-phenotyping treatment modifiers.

Phenotypic variable	Expected treatment-phenotype interaction	Mechanistic Role
Patient pain catastrophizing score	MBSR	Moderator
Patient experience score	MBSR	Mediator
Fear avoidance beliefs score	PT/Exercise	Mediator
PROMIS self-efficacy score	PT/Exercise	Moderator
Fibromyalgia Screening Questionnaire	Acupressure	Moderator
Biologic Sex	Acupressure	Moderator
Fibromyalgia Screening Questionnaire	Duloxetine	Moderator
PainDETECT score	Duloxetine	Moderator

Table 3 Hypothesized deep-phenotyping treatment modifiers.

Deep Phenotype variable	Measurement Modality	Expected treatment-phenotype interaction	Mechanistic Role
Subgenual ACC activity	fMRI	MBSR	Moderator
Ventrolateral PFC activity	fMRI	MBSR	Moderator
S1 activity	fMRI	MBSR	Moderator
Thalamus activity	fMRI	MBSR	Moderator
Baseline activity	Actigraphy	PT/Exercise	Moderator
Parasympathetic tone	Heart Rate Variability	PT/Exercise	Moderator
Vagal Tone	EKG and PPG	PT/Exercise	Mediator

High Basal Inflammation	Blood Sample	PT/Exercise	Moderator
Pain Threshold	QST	Acupressure	Moderator
Posterior Insula Glutamate	H-MRS	Acupressure	Moderator
Insula-DMN connectivity	fMRI	Acupressure	Moderator
DMN-SI connectivity	fMRI	Acupressure	Moderator
Deficient Lower Back Pain Inhibition	QST	Duloxetine	Moderator
Lesser PAG-Insula connectivity	fMRI	Duloxetine	Moderator
Elevated Stimulated inflammatory response	Blood Sample	Duloxetine	Moderator

We plan to conduct a single subgroup analysis that will assess whether males and females differentially respond to the proposed treatments.

In addition to the covariates listed above, the following biological variables will be controlled for in the primary analysis: sex, age, BMI, race, and education.

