6.8 Actigraphy and Ecological Momentary Assessment (EMA)

After completing the screening/baseline activities, participants will receive instruction on the use of the PRO-Diary monitor, which the participant will wear during 5 separate 7-day “home monitoring” periods, at baseline (sent home with watch following baseline visit) and T2-T5 to assess physical activity (objectively measured via accelerometry), and ecological momentary assessment (EMA) of mental and physical symptoms. EMA will be collected during Weeks 1, 6, 15, 24 and 36).

To measure real-time physical activity and collect ecological momentary assessment data, we will utilize the PRO-Diary (Figure 5 <http://www.camntech.com/products/pro-diary/pro-diary-overview>), a wrist-worn accelerometer with a touch-screen user-interface. The PRO-Diary collects physical activity data (via a triaxial MEMS accelerometer) as ‘activity counts’ during regular epochs during the home monitoring period and stores time-stamped self-report data until the participant returns the watch to the lab, where the data will be downloaded for cleaning and analysis.

EMA data will be collected using a wrist-worn PRO-Diary or by distributing surveys via text message through Qualtrics. EMA ratings at wake and bedtime will be initiated by the participant upon waking (not necessarily when they get out of bed) and at bedtime (“lights out” or the time they intend to go to sleep, not necessarily the

Figure 5 Pro-Diary- a wrist accelerometer

time they get into bed). An audible alert (beep) or vibration will alert participants to enter midday ratings; the PRO-Diary will be programmed to deliver the alert at a random time each day between 11:00AM and 3:00PM. The PRO-Diary will display a reminder message to complete bedtime ratings at 8:00PM each day.

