6.8.1 Physical activity

The PRO-Diary will collect physical activity data as ‘activity counts’ during regular 15-second epochs at a sampling rate of 50 Hz⁷⁶ during the home monitoring period and store time-stamped self-report data until the participant returns the device back to the lab, where the data can be downloaded for cleaning and analysis. The home monitoring period is 7 days which is recommended to obtain a habitual activity profile and will help control for missing data as literature supports a minimum of 5 days of data needed for valid physical activity measurement in adults.⁷⁷ We will require 10 hours of data/day to be considered valid per recommended guidelines.⁷⁸ Activity counts per minute will be aggregated using custom-set intervals surrounding the EMA ratings. Specifically, these activity counts will be averaged in windows around each EMA rating to provide an estimate of activity that was relatively concurrent with the ratings. This will allow for examination of pain intensity and interference in the context of changes in physical activity. Average activity counts per minute for the entire assessment period will also be calculated to assess overall pre- to post-treatment changes in physical activity. Other physical activity variables that will be generated in aggregate with EMA and over the whole assessment period include: percent time immobile (an index of sedentary behavior) and maximum activity counts (an index of top physical activity intensity).

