18.1.2 PT/exercise

Predictors of response in light phenotyping (Aim 2). Most of the studies to date that have attempted to identify factors most predictive of differential responsiveness to exercise in cLBP have been based on some variation of the cognitive behavioral fear avoidance model, wherein low functional self-efficacy for exercise is related to high pain catastrophizing and fear of movement.⁹³⁻⁹⁷ This cognition has been shown to promote the transition from acute to chronic low back pain, as well as to be associated with worse chronic low back pain.⁹⁷⁻⁹⁹ Our primary hypothesis for the light phenotyping protocol is those individuals with the *highest scores on the Fear Avoidance Beliefs Questionnaire (FABQ)* and *lowest scores for PROMIS Self-Efficacy for Managing Symptoms* will be most likely to improve from our PT program, which is focused on getting participants over this fear of movement.

Predictors of response in deep phenotyping (Aim 3). Studies using QST or functional neuroimaging have suggested that aerobic exercise may lead to pain improvement in part via augmentation of descending analgesic pathways.¹⁰⁰⁻¹⁰³ This is also supported by the fact that humans and animals who are actively exercising are less pain sensitive (mainly to mechanical stimuli) than controls.¹⁰⁴⁻¹⁰⁷ Both opioidergic and non-opioidergic (e.g. norepinephrine) pathways are believed to exert these effects. Furthermore, elevated basal inflammation (e.g., CRP, IL-6) is associated with both the presence and severity of cLBP even after adjustment for potential confounding variables like obesity.^{108,109} However, the exercise programs used in cLBP (and proposed in our MRC) are rarely aiming to get patients to do aerobic exercise. Instead, these programs initially focus on stretching and strengthening, as well as encouraging more activity and movement. We feel that the E4 device we propose to use in deep phenotyping will give us two measures that will predict responsiveness to our PT/exercise program: *low baseline activity levels* as measured by the actigraph, as has been previously shown,^{96,110} as well as *low parasympathetic tone* as measured by the heart rate variability high frequency (HF)

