## 5.6 Study Assessments

Table 1 shows the schedule of assessments for screening, demographic data, outcomes, and light and deep phenotyping. Measurements at T2-T5 may occur within a target observation window around each nominal study sample time ( $\pm 2$  weeks). A subset of 160 eligible subjects enrolled in the clinical trial will undergo deep phenotyping.

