### 9.1.2 Deep Phenotyping Analysis

A second analysis will assess whether deep-phenotyping measures are also predictive of differential treatment response. The form of the model will be nearly identical to the light phenotype-based primary analysis above. The analytic plan and strategy for performing inference on model parameters is the same as stated above in 9.1.1. The primary difference between the primary and secondary analysis is the number of treatment modifiers that were proposed by investigators. As a result, the deep phenotyping-based model will include multiple treatment-phenotype interaction terms for each treatment arm (see Table 5). *Table 5 Hypothesized differential responses to treatment*

Deep Phenotype variable	Measurement Modality	Expected treatment-phenotype interaction	Mechanistic Role
Subgenual ACC activity	fMRI	MBSR	Moderator
Ventrolateral PFC activity	fMRI	MBSR	Moderator
S1 activity	fMRI	MBSR	Moderator
Thalamus activity	fMRI	MBSR	Moderator
Baseline activity	Actigraphy	PT/Exercise	Moderator
Parasympathetic tone	Heart Rate Variability	PT/Exercise	Moderator
Vagal Tone	ECG and PPG	PT/Exercise	Mediator
High Basal Inflammation	Blood Sample	PT/Exercise	Moderator
Pain Threshold	QST	Acupressure	Moderator
Posterior Insula Glutamate	H-MRS	Acupressure	Moderator
Insula-DMN connectivity	fMRI	Acupressure	Moderator
DMN-SI connectivity	fMRI	Acupressure	Moderator
Deficient Lower Back Pain Inhibition	QST	Duloxetine	Moderator
Lesser PAG-Insula connectivity	fMRI	Duloxetine	Moderator
Elevated Stimulated inflammatory response	Blood Sample	Duloxetine	Moderator

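### Baseline activity is tested as a PT/exercise moderator only in the 160 deep-phenotyping patients, although the protocol plans accelerometry for every participant

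*SAP*

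**What the plan says.** SAP 7.3 splits the hypothesised modifiers into a light list (Table 2) and a deep list, "Table 3 Hypothesized deep-phenotyping treatment modifiers". The row "Baseline activity Actigraphy PT/Exercise Moderator" is in the deep list, and Table 2 has no activity variable. SAP 9.1.2 repeats the row as "Baseline activity" in Table 5 and describes the model that uses the list: "A second analysis will assess whether deep-phenotyping measures are also predictive of differential treatment response". On numbers, SAP 5.6 states: "A subset of 160 eligible subjects enrolled in the clinical trial will undergo deep phenotyping". SAP 6.1 takes this as 40 patients per treatment, against 102 per treatment for light variables.

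Protocol 6.8, part of the baseline visit for the whole cohort, says that "participants will receive instruction on the use of the PRO-Diary monitor". The monitor is worn for 7 days at baseline and again at T2 to T5, and one stated purpose is to measure physical activity by accelerometer. Protocol 6.8.1 defines the summary measure: "Average activity counts per minute for the entire assessment period will also be calculated". It requires 10 hours of data for a valid day and cites 5 days as the minimum for valid measurement.

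The link to deep phenotyping comes from Protocol 18.1.2: "the E4 device we propose to use in deep phenotyping will give us two measures that will predict responsiveness". Low baseline activity is one of those two measures.

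**The concern.** A named, directional hypothesis is assigned to about 39% of the patients in whom the plan intends to measure the variable. The stated source device does not appear in the deep-visit procedures (Protocol 10) or in the deep-phenotyping rows of either schedule. Autonomic signals there come from a BIOPAC system during scanning (Protocol 10.2.3), and no activity recorder is described.

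The SAP gives the modality as actigraphy, and the only actigraphy procedure in the documents is the cohort-wide one in Protocol 6.8. The placement therefore looks like a leftover from a device that was once proposed. At stake are the precision of one pre-specified interaction and the size of the deep model, which carries 15 modifier rows for 160 patients.

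**Working it through.** **Inputs.** From SAP 6.1: two-sided 5% test; light variables n = 102 per arm, r = 0.28, power at least 80%; deep variables n = 40 per arm, r = 0.42, power 80%. From SAP 5.5 and 5.6: 408 randomised, 160 deep. From SAP 7.4: no more than 15% missing data expected.

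**Formula.** Fisher z: power ≈ Φ(atanh(r)·√(n−3) − 1.96), ignoring the negligible opposite tail.

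**Reproducing the SAP's figures.**
- n = 102, r = 0.28: 0.2877 × 9.950 − 1.96 = 0.902, giving 81.7%. This agrees with at least 80%.
- n = 40, r = 0.42: 0.4477 × 6.083 − 1.96 = 0.763, giving 77.7%. It is 78.7% with the small-sample bias term, 78.6% by simulation and 81.4% by noncentral t. The stated 80% lies within this spread.

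**Deep subset against full arm, for the same variable.**

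| True r in the PT arm | n = 40 | n = 102 | n = 87 (15% lost, assumed) |
|---|---|---|---|
| 0.28 | 41.7% | 81.7% | 75.1% |
| 0.30 | 46.9% | 86.9% | 81.0% |
| 0.35 | 60.4% | 95.3% | 91.8% |
| 0.42 | 77.7% | 99.4% | 98.4% |

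Here 102 × 0.85 = 86.7, taken as 87. If the deep arm lost the same share (40 × 0.85 = 34), its power at r = 0.28 would be 36.0%. The correlation detectable with 80% power is 0.43 at n = 40 and 0.27 at n = 102.

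**Precision, whatever the effect.** 160/408 = 0.39, and √(408/160) = 1.60.

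**Interaction, which is what the SAP tests.** Assume a unit-variance modifier and no slope in the other three arms. The slope-difference standard error, in residual SD units, is √(1/40 + 1/120) = 0.183 for the deep subset and √(1/102 + 1/306) = 0.114 for the full cohort.
- Slope r, residual SD √(1 − r²/4), r = 0.28: 0.28/(0.183 × 0.990) = 1.55, giving 34%; 0.28/(0.114 × 0.990) = 2.47, giving 70%.
- Slope r/√(1 − r²) = 0.292, residual SD 1: 36% and 72%.
- First version at r = 0.42: 65% and 96%.

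All these figures use stage-1 patients only. The planned model pools T3 and T4 under a common interaction, so its absolute power would differ in both columns.

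**The case against.** The strongest case against has four parts.

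- **A reason is documented.** A reader might infer that the restriction is arbitrary. The documents do not support that: Protocol 18.1.2 ties the measure to a deep-phenotyping device, and SAP 7.3 refers the reader to Protocol 18.1. What remains is that no current procedure or schedule section describes the device.
- **The loss depends on the effect.** A reader might say that the restriction halves power. That is roughly so within the arm only near r = 0.28 to 0.30. At r = 0.42, the SAP's own planning effect for deep variables, the loss is about 22 points. The 1.6-fold standard error does not depend on the effect, and SAP 7.5 intends to present results as confidence intervals rather than p-values.
- **Valid actigraphy may not exist for all 408.** Protocol 6.8 lets EMA be collected by text message, which yields no accelerometry, and the wear rules will remove some records. Payments and schedule rows refer to EMA, not to wearing the accelerometer. This stands, and it is why the n = 87 column is shown. Nothing exempts deep patients from the same gap if the PRO-Diary is the source.
- **The consequence is limited.** This is one of 15 deep rows, in what SAP 9.1.2 itself treats as secondary, with no multiplicity control. Aim 2 lists ambulatory monitoring among predictors for all patients, and exploratory Objective 2 screens further light predictors. Neither names actigraphy, so neither replaces the pre-specified test.

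**Conclusion.** The point holds as an inconsistency with a real cost in precision. The plan collects baseline activity from the cohort but confines its named test to the deep subset, on the strength of a device that the procedures do not describe. The standard error is about 1.6 times what the full cohort would give. Within-arm power is about 42% against 82% at r = 0.28 and 78% against 99% at r = 0.42; the interaction at r = 0.28 has about 34–36% against 70–72%.

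These figures assume stage-1 data only, no slope in the other arms for the interaction, and complete actigraphy except where a 15% loss is stated. The change should be made before analysis. It does not call the trial's other tests into question.

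**What to change.** 1. State in the SAP that the PRO-Diary supplies baseline activity.
2. Move the baseline activity × PT/exercise interaction from Tables 3 and 5 to Table 2 and the section 9.1.1 model, analysed in all randomised patients with valid wear.
3. Define the variable as mean activity counts over the T1 (week 1) wear period, with at least 5 valid days of 10 hours each. That period precedes allocation. The week-6 period falls in the same week as the T2 visit, where randomisation takes place, so it may not.
4. Section 9.1.1 indexes modifiers at times 2 and 3. State that the T1 value is carried unchanged into both the T3 and T4 equations, and change the stated 7 columns and 8 interactions to 8 and 9.
5. If a separate device is in fact used at deep visits, describe it and justify the restriction instead.

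The cost is SAP wording, with no new data collection. The light model gains one main effect and one interaction, and some patients will lack valid actigraphy and fall under the missing-data rules in SAP 7.4. The deep model drops from 15 modifier rows to 14.

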8.1 Criteria for randomization

Randomization will occur at T2 and T3 study visits. Participants with minimal or modest improvement in pain after the PainGuide run-in (PGIC \geq 2) will be randomized. Participants who have a robust improvement in their pain (PGIC<2) will not be randomized to treatment. These non-randomized participants will still complete the remaining study visits and mini-assessments. In order to assign equal numbers of participants to each of the 4 study interventions, randomization probabilities will account for the fact that certain participants, e.g. because of a contraindication, may be eligible for only 3 of the 4 treatments.

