## 5 Study Methods

### 5.1 General Study Design and Plan

We will conduct a 36-week pragmatic trial in a cohort of cLBP patients (see Figure 1 and Figure 2). The proposed SMART will consist of a 4-week run-in period using an online cognitive-behavioral self-management intervention (PainGuide), followed by two 8-week treatment periods. All participants will be followed for a total of approximately nine months.

At baseline (T1), approximately 500 patients will undergo a comprehensive baseline phenotyping assessment. After receiving PainGuide (access to an online self-management program) for 4 weeks, each participant will complete a light phenotyping assessment (T2) and a subset of these patients (n=160) will complete an additional deep phenotyping assessment. Those who still have significant pain interference ( $\geq 2$  from Patient Global Impression Scale, PGIC) will be randomized to one of the four 8-week long interventions (i.e., Mindfulness-Based Stress Reduction (MBSR), Physical Therapy (PT)/Exercise, Acupressure self-management [eHealth app], or Duloxetine). Participants with a PGIC=1 will not be randomized and continue with long-term follow-up. The PainGuide run-in is designed to provide the lightest “touch” intervention and to help control for regression to the mean. We will use block randomization with random block size of 4 and 8. Approximately 102 patients will be assigned to each treatment group including Physical Therapy/Exercise, MBSR, Acupressure, and Duloxetine treatment groups. For addition details, please see Section 6.3.

Following the first 8-week treatment period, patients will be reassessed (T3) using light only or light plus deep assessments (for the subset of 160) and those still having significant pain interference ( $\geq 2$  from Patient Global Impression Scale [PGIC]) will be re-randomized to receive one of the three treatments they did not receive in the first treatment period. Participants with a PGIC=1 will not be randomized and continue with long-term follow-up. After the second intervention and three months later, all undergo the light phenotyping follow-up assessment protocol (T4). Lastly, a final assessment will take place at 3 months after the scheduled end of the second 8-week treatment period (T5). There will also be a series of interim assessments that take place at 2-week intervals in between the regular assessments (T1-T5).

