#### **5.4.2 Inclusion Criteria for Light Phenotyping**

- We will use the definition of chronic low back pain (cLBP) described in the NIH Task Force Report on Research Standards for Chronic Low Back Pain, i.e. low back pain present at least six months, and present more than half of those days.
- Individuals must have a pain interference score of  $\geq 60$  on PROMIS Pain Interference at T1 for inclusion. The normal population mean and standard deviation for the PROMIS Pain Interference measures are 50 and 10 points, respectively. Therefore, participants must be 1 SD above the population mean ( $>=60$ ) for inclusion.
- Individuals must be willing and eligible to be randomized to receive at least three of the four proposed treatments.

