#### **5.4.4 Contraindication to study interventions**

##### **5.4.4.1 Duloxetine**

- Contraindications to receiving duloxetine:
  - Medications such as:
    - Lithium
    - Tramadol (Ultram, Ultracet)
    - St. John's Wort
    - Prochlorperazine (Compazine)
    - Thioridizine (a psychiatric medication)
    - Propafenone or Flecainide (for heart rhythm problems)
    - Ciprofloxacin (Cipro, an antibiotic)
    - Linezolid (Zyvox, an antibiotic)
    - Methylene Blue
    - Cimetidine (Tagamet, for heartburn)
    - Clomipramine (Anafranil)
    - Vortioxetine (Trintellix)
    - SSRIs:
      - sertraline
      - paroxetine
      - fluoxetine
      - escitalopram
      - citalopram
      - fluvoxamine
    - SNRIs:
      - Venlaxaxine
      - Milnacipran
      - Duloxetine
      - Sibutramine
      - Atomoxetine
      - Desvenlafaxine
      - Levomilnacipran
  - Renal dysfunction: Creatinine Clearance <30mL/min or End-Stage Renal Failure
  - Hepatic dysfunction: Liver function tests (LFTs) elevated times 1.5
  - History of allergy to duloxetine
  - History of bipolar disorder

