##### **5.4.4.2 Acupressure**

- Currently receiving acupressure or acupuncture through a formal therapy

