### **5.5 Randomization and Blinding**

Blocked randomization will be used for the randomization schedule. Block size will be randomized between 4 and 8 and the ordering of treatment assignments within a block will be random.

Randomization will be performed without stratification. Study recruitment will continue until 408 patients have been randomized into a treatment group at study phase T2. We expect that it will be necessary to recruit approximately 500 patients into the study in order to achieve the target of 408 SMART participants. Based on our previous studies , we expect that approximately 15-20% of patients recruited at study phase T1 will not enter the SMART at study phase 2 due to either response to the PainGuide self-management intervention or withdrawal from the study.

We will perform randomization using a randomization software or a randomization list created by a statistician to assign participants to a treatment in an unbiased manner. A biostatistician will develop the randomization plan and will create the un-blinded randomization list to be uploaded to the software. This will enable study personnel to obtain treatment allocations and will provide functionality to manage the treatment allocation process. Furthermore, this enables study team members to maintain identifying information from participants. The randomization software will also track study treatment-allocation progress and provide documentation of the treatment assignment.

Randomization at T3 will be done similar to the one at T2.

Due to the nature of the study and its interventions, neither patients nor study staff will be blinded

to patients' treatment assignments.

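### Allocation is random only within eligibility set, but the SAP 9.1.1 and 9.2 models have no eligibility term, so treatment main contrasts are open to confounding; separately, the printed T4 equation omits stage-1 treatment

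*SAP*

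**What the plan says.** - **Entry and allocation.** SAP 5.4.2: "Individuals must be willing and eligible to be randomized to receive at least three of the four proposed treatments". Protocol 8.1 aims at equal arms and says that the randomization "probabilities will account for the fact that certain participants, e.g. because of a contraindication, may be eligible for only 3 of the 4 treatments". SAP 5.5 says "Randomization will be performed without stratification" and "Block size will be randomized between 4 and 8", and does not mention eligibility.
- **Who can be barred.** SAP 5.4.4 lists bars for every arm. The entry "Contraindications to receiving duloxetine" covers SSRIs, SNRIs, tramadol, lithium and other drugs, renal and hepatic dysfunction, allergy and bipolar disorder. Acupressure has one entry ("Currently receiving acupressure or acupuncture through a formal therapy"), MBSR one and PT two. No prevalence is given for any of them.
- **Adjustment.** SAP 7.3: "In addition to the covariates listed above, the following biological variables will be controlled for in the primary analysis: sex, age, BMI, race, and education". The 9.1.1 model adds the T2 score and seven hypothesized modifiers. The 9.2 model uses the same baseline set plus penalized further predictors. Neither has an eligibility term.
- **Second stage.** Under SAP 5.1, patients still in pain at T3 "will be re-randomized to receive one of the three treatments they did not receive in the first treatment period". In 9.1.1 the printed equation for the T4 mean has stage-2 treatment (A3) in every treatment term and stage-1 treatment (A2) in none. In 9.2 the response-status bracket holds A2, in order to adjust T4 for the first treatment. The 9.1.1 text also lets treatment main effects differ between stages.

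**The concern.** A patient barred from duloxetine can never be in the duloxetine arm, so such patients collect in the other three arms. The design produces this imbalance, and a larger sample does not reduce it. Antidepressant or tramadol use could plausibly be related to later pain interference, and the five demographic covariates do not capture it. The T2 score and the modifiers may capture part.

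Treatment main effects are among the quantities that the 9.1.1 joint model is meant to estimate. The 9.2 predictions under each of the four treatments for every patient also rest on them.

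The T4 equation raises a different question. The first treatment determines which second treatments are open, so A3 depends on A2. If A2 is left out of the T4 mean, carry-over from stage 1 can appear as a stage-2 treatment difference. Section 11 plans to compare the 12 embedded regimens with this model.

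**Working it through.** **The plan's own figure.** SAP 6.1 states at least 80% power for r = 0.28 with 102 patients. Fisher z gives Phi(atanh(0.28) x sqrt(99) - 1.96) = 81.7%, which agrees. For r = 0.42 with 40 patients it gives 77.7% (81.4% by noncentral t), so the stated 80% there depends on the method.

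**Inputs (all assumed; none is in the documents).** p = share barred from one arm; q = fraction of those barred from duloxetine, the rest spread evenly over the other arms; d = points by which barred patients score worse at T3 after adjustment; c = carry-over of a stage-1 arm to T4. Residual SD 7, so d = 3 is 0.43 SD.

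**T3 duloxetine contrast.** With equal arms and barred patients uniform over their three open arms, the barred share is 4p(1-q)/3 in the duloxetine arm and 4p(2+q)/9 in each other arm. The difference times d gives

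bias = -(4p/3) x d x (4q-1)/3.

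A negative value flatters duloxetine. At q = 1 this is -(4p/3)d:

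| p | d = 1 | d = 2 | d = 3 |
|---|---|---|---|
| 10% | -0.13 | -0.27 | -0.40 |
| 20% | -0.27 | -0.53 | -0.80 |
| 30% | -0.40 | -0.80 | -1.20 |

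At p = 30% and d = 3 it falls to -0.80, -0.40 and 0 for q = 75%, 50% and 25%. Simulations of the T3 model (n = 408, no true treatment effect, q = 1, d = 3) gave -0.37 to -0.41, -0.78 to -0.80 and -1.13 to -1.23 at p = 10, 20 and 30%. With an eligibility indicator the bias was within about 0.06 of zero.

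**Tested interactions.** For the fibromyalgia score by duloxetine, with barred patients 0.5 SD higher on the score and q = 1, the |W| >= 2 rule rejected in 5.2, 6.2 and 7.2% of runs at d = 3 (p = 10, 20, 30%) and in 5.2-5.6% at d = 1. With the indicator the range was 4.8-5.4% (Monte Carlo error about 0.4 points). With the score unrelated to eligibility the rate was 5.5%. Harsher assumptions (20-40% barred, gap 0.3-0.5 SD, latent correlation 0.4 between modifier and eligibility) gave 6.7-10.4%.

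**Best-treatment step.** In an ordinary least squares stand-in for 9.2 with no true treatment differences and q = 1, the share of patients whose lowest predicted score fell under duloxetine was 28, 31 and 33% (d = 1) and 33, 43 and 52% (d = 3) at p = 10, 20 and 30%. With the indicator it was about 25%. This is not the elastic net of 9.2, so it shows direction only.

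**T4 equation.** If responders have no second treatment, the printed R x A3 block is identically zero and its coefficients cannot be estimated. Among non-responders with second treatment j, nobody had j first. Among those with another second treatment, one third had j first. Leaving out A2 therefore biases the stage-2 contrast of arm j by -c/3. If 10-30% are barred from duloxetine at both stages, the third becomes 0.32-0.29 for duloxetine and 0.34-0.35 for the other arms. If the T3 modifiers absorb a share s, the bias is -(c/3)(1-s). For c = -2 this is +0.67, +0.50, +0.33 and +0.17 at s = 0, 25, 50 and 75% (simulated 0.65, 0.49, 0.34 and 0.14; -0.03 at s = 0 with A2 terms added).

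In a simplified joint fit as printed (c = -2, 11% responders), the T3 duloxetine contrast moved by only -0.01 to +0.01 and the interaction tests rejected in 4.7-5.6% of runs. Replacing A3 by A2 in the brackets does harm: with an assumed -2 duloxetine effect at stage 2 only, it biased the T3 contrast by -0.81, whereas adding A2 alongside A3 left it near 0.

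**The case against.** The strongest objection is that the planned inference barely depends on these contrasts. SAP 9.1.1 tests only the treatment-by-phenotype interactions, and no test of treatment main effects is planned. The 9.2 subgroups are descriptive and meant to generate hypotheses, and Section 11 is exploratory. This stands, and it limits the severity.

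Every magnitude also rests on assumed inputs. A longer contraindication list does not show that more patients are barred, and the T2 score, the modifiers and mood measures among the 9.2 predictors may absorb part of the gap, although penalized terms can be dropped. This stands too: the documents support open to confounding, not biased.

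A reader might infer three stronger points that the documents do not support:

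- **That the primary interaction tests are invalid.** They are disturbed only if eligibility is related to the modifier or changes its slope, and then modestly over the main range examined.
- **That SAP 5.5 contradicts Protocol 8.1.** Unstratified blocks do not exclude eligibility-dependent probabilities, and SAP 5.5 leaves the mechanics to a statistician's randomization plan. What is missing is an explanation.
- **That the missing A2 undermines the T3 results.** Stage-2 effects vary freely in the joint model, which shields the T3 contrasts, and SAP 9.1.1 also has a stage-1-only fallback. The printed A3 may be a subscript slip. It could also be meant to let main effects differ by stage, but that reading still leaves no stage-1 treatment in the T4 mean.

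**Conclusion.** The point holds, at minor to moderate severity. T2 allocation is random only within eligibility set and neither model accounts for it. The treatment main contrasts and the 9.2 predictions built on them are open to confounding if barred patients differ in outcome after adjustment. That duloxetine is the most exposed arm is an inference from its contraindication list. Under the assumed ranges (10-30% barred, all from duloxetine, gap 1-3 points) the T3 duloxetine contrast is off by about -0.13 to -1.2 points, and by nothing if there is no gap or the bars are spread evenly.

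The T4 equation is a separate and minor matter. Any harm is confined to stage-2 main contrasts and the exploratory regimen comparisons.

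**What to change.** 1. Add eligibility-set indicators to 9.1.1 and 9.2: the set in force at T2 for the T3 outcome and the set in force at T3 for the T4 outcome, since each governs its own randomization. No passage says how often eligibility changes between the two. In the deep analysis, use one barred-from-duloxetine indicator if sets are sparse.
2. As a sensitivity analysis, restrict each contrast to patients eligible for both arms compared.
3. State in SAP 5.5 how blocks of 4 and 8 operate with the Protocol 8.1 probabilities.
4. In the 9.1.1 equation for T4, add R x A2 and (1-R) x A2 and keep the (1-R) x A3 term, so that main effects may still differ between stages. Do not simply replace A3 by A2. State how long-term follow-up (SAP 7.2.1) is coded, because 9.1.1 defines only four treatment elements. Settle this before the model is used for Section 11.

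**Cost.** SAP wording and a few model terms. Eligibility per arm must be known to apply the three-of-four rule, so the sets should be derivable, although no passage names a data field. One indicator raises the simulated duloxetine main-contrast standard error by about 2, 4 and 7-8% at p = 10, 20 and 30%, and the interaction standard error by under 1%. Fisher z power, charging the parameters to one arm, goes from 81.7% to 81.3% in the light analysis and from 77.7% to 76.6% in the deep analysis. Four to six parameters would give 80.1-79.2% and 73.0-70.3%, which is why the deep model should collapse to one.
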